Importantly, we will explore the dyadic effects of couple members' simultaneous engagement in the MBSR intervention. In addition to using proper statistical techniques to understand the effects of MBSR on each partner's outcomes, we will examine partner influences. For each primary hypothesis, we will examine the secondary hypothesis that each partner's improvement in each health outcome (self-report physical health, stress, mindfulness, and metabolic syndrome composite biomarker score) will be associated with improvement in the other partner's health outcome. In addition, we will examine the effects of the intervention on both partners' relationship satisfaction. Showing that relationship satisfaction can be enhanced is an important goal on its own, but we may also find that health outcomes improve when relationship quality improves.

3. Research Plan:

Procedures

Forty couples (N=80) will participate in a baseline visit to have blood drawn, BMI and BP measured, and to complete questionnaires assessing demographics, contextual factors, and baseline primary outcomes. Couples will be randomized to the MBSR condition (n=20 couples/ 40 individuals) or the wait list control condition (n=20 couples). The baseline blood draws and survey administration will take place at the CSRU, with the HRU as back up as needed. The blood analysis will be done by the YCCI Core lab. All participants will receive an informational sheet about metabolic syndrome.

Participants will be randomized to the intervention or wait-list group after informed consent is obtained, the initial blood is drawn and survey baseline is completed at the CSRU. A random digit generator will be used that assigns a condition (in this case, intervention or wait list) to each couple ID number.

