MBSR condition: MBSR is a standardized protocol consisting of 8-weekly 2.5 hour sessions, homework consisting of 30-45 minutes of mindfulness meditation practice six days per week and a one-time half-day (4-6 hour) retreat. This will be offered at the Social Gerontology and Health lab, [name] Our MBSR intervention is based upon the standard regimen taught at the University of Massachusetts.(Kabat-Zinn, 2013) Participants will attend weekly group sessions at the Yale Stress Center at the Yale School of Medicine taught by an experienced MBSR instructor ([name] MA MSW) who collaborates closely with Co-I [name]. Each weekly session will consist of an instructor-led mindfulness meditation, followed by a discussion of the meditation and its application into participants' everyday life. Formal meditations that will be led and discussed include eating meditation, body scan, sitting meditation, Hatha Yoga, and walking meditation. Participants will take their partners blood pressure reading with an automated Carescae cuff at each MSBR class. In addition, informal mindfulness practices of awareness of pleasant and unpleasant events and awareness of routine events will be discussed. Participants will be recording their daily mindfulness practice minutes on attached form.

Wait list condition: After the MBSR condition groups have completed their sessions, the participants in the Wait List group may choose to participate in the 8-week MBSR class. Participants will be provided with a coupon to participate starting July 2018. In the meantime, participants in the Wait list group will complete the same measures at the same time points as participants enrolled in Cohort 1 and Cohort 2 of the MBSR conditions.

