How quantitative and qualitative data will be combined to understand outcomes. Qualitative data will be analyzed using Atlas.ti software and themes will be identified regarding partner influence on study experience. Key demographic characteristics and results from quantitative questions regarding decision making in participation and adherence will be entered into the software as coded attributes. Queries will be conducted to investigate the relationships between identified themes and coded attributes. Finally, the results of this qualitative analysis will be used to formulate hypotheses about the meanings and mechanisms underlying the quantitative results for Hypotheses 1 and 2, and especially, for the results of dyadic analyses of couple members' simultaneous engagement in the MBSR intervention.

Power: The sample size procedure in PASS shows that in anticipation of loss-to-follow-up, and with recognition of dependency in results from couples, the effective sample size is estimated to be 70, a reduction of 10 from the enrollment of 80 study participants. Assuming power of 80%, an outcome standard deviation of 10, and equal assignments to the intervention and control groups, this effective sample size will allow for detection of a difference between intervention and control groups mean values for the SF-12 outcome of 6.43 or more at the two-sided level of significance of 0.05. The sample size procedure in PASS was performed.

SECTION III: RECRUITMENT/CONSENT AND ASSENT PROCEDURES

1. Targeted Enrollment: Give the number of subjects: 80 participants

- a. Targeted for enrollment at Yale for this protocol: 80
- b. If this is a multi-site study, give the total number of subjects targeted across all sites: N/A

2. Indicate recruitment methods below. Attach copies of any recruitment materials that will be used.

- | | | |
|---|---|-------------------------------------|
|  Flyers |  Internet/Web Postings |  Radio |
|  Posters |  Mass E-mail Solicitation |  Telephone |
|  Letter |  Departmental/Center Website |  Television |
|  Medical Record Review* |  Departmental/Center Research Boards |  Newspaper |

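### The stated randomisation mechanism carries no restriction, so the planned 20/20 split of couples, and balance within each MBSR cohort, is left to chance

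*Protocol*

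**What the plan says.** Protocol, Section I, item 3 (Research Plan, Procedures) sets the sample: "Forty couples (N=80) will participate in a baseline visit". It fixes the allocation: "Couples will be randomized to the MBSR condition (n=20 couples/ 40 individuals) or the wait list control condition (n=20 couples". It then gives the mechanism: "A random digit generator will be used that assigns a condition (in this case, intervention or wait list) to each couple ID number". Assignment follows baseline: "Participants will be randomized to the intervention or wait-list group after informed consent is obtained", and also after the first blood draw and survey.

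The paragraphs on the two conditions add that the intervention is taught to groups, "Participants will attend weekly group sessions at the Yale Stress Center", and that the wait-list arm is measured in step with "participants enrolled in Cohort 1 and Cohort 2 of the MBSR conditions". Cohort sizes are not given.

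The Power paragraph in item 13 (Statistical Considerations) relies on equal arms: "Assuming power of 80%, an outcome standard deviation of 10, and equal assignments to the intervention and control groups".

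The protocol mentions no blocking, stratification, cap or list with a fixed number per arm.

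**The concern.** The same paragraph states a fixed result and a method that, taken at its word, does not produce it. If a condition is drawn separately for each couple, the number in the MBSR arm is a binomial count, not 20. With only 40 couples, that count varies noticeably.

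Three things are at stake:
- **Precision.** Unequal arms lose some of it, and the power statement assumes they are equal.
- **Balance over time.** The arms may be unevenly spread over the two cohorts.
- **Class size.** MBSR is delivered to groups, so the number of couples allocated to it within a cohort decides how large the classes are. Feasibility of MBSR for couples is Aim 1, so class size matters in its own right.

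**Working it through.** **Inputs from the protocol.** 40 couples; 20 planned per arm; one condition generated per couple ID; two MBSR cohorts; power 80%, SD 10, two-sided 5%, effective sample size 70, detectable difference 6.43.

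**Assumptions.** Draws are independent with probability 0.5, because the protocol states neither independence nor the probability. For the cohort figures, each cohort has 20 couples, counting both arms, and the MBSR couples of a cohort form one class.

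**The plan's own figures.** The counts agree: 20 + 20 = 40 couples = 80 people. The detectable difference does not reproduce. With 35 per arm, 10 × (1.960 + 0.842) × √(2/35) = 6.70, not 6.43. That is a separate matter, unrelated to the randomisation method. Below I take a design with exactly 80% power at 20/20 and ask what unequal arms cost it.

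**Chance of the planned split.** With X ~ Binomial(40, 0.5), P(X = 20) = C(40,20)/2^40 = 0.1254. Relative efficiency of a split a/b is 4ab/40². Power is for a two-sample comparison of means (normal approximation) with effective N of 70 divided in the same ratio.

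| Split | Chance of this or worse | Efficiency | Power |
|---|---|---|---|
| 20/20 | – | 100% | 80.0% |
| 18/22 | 63.6% | 99% | 79.6% |
| 16/24 | 26.8% | 96% | 78.4% |
| 14/26 | 8.1% | 91% | 76.2% |

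At 14/26 the detectable difference grows by a factor of 1/√0.91 = 1.05. The range from 14 to 26 couples in one arm covers 96% of draws.

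**Averages over all splits.** E[X(40 − X)] = 40 × 20 − (10 + 400) = 390, so expected efficiency is 4 × 390/1600 = 97.5%. Expected power is 79.0%.

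**Within cohorts (20 couples each, assumed).** P(10/10) in one cohort = C(20,10)/2^20 = 17.6%; in both, 0.176² = 3.1%. A split of 7/13 or worse has probability 26.3% in one cohort, and 1 − (1 − 0.263)² = 45.7% in at least one of the two. An MBSR class would hold 6 to 14 couples (12 to 28 people) in about 96% of draws.

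**Permuted blocks within cohort (simulation, 20,000 runs per row).**

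| Block sizes | Cohort sizes | Exactly 20/20 | Within one couple per arm |
|---|---|---|---|
| 4 | 20 + 20 | 100% | 100% |
| 4 | 18 + 22 | 50% | 94% |
| 2 and 4 mixed | 20 + 20 | 81% | 99% |
| 2 and 4 mixed | 18 + 22 | 80% | 99% |
| 2 and 4 mixed | 19 + 21 | 50% | 100% |

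Exact equality depends on whether each cohort ends on a complete block. With mixed blocks of 2 and 4, the split stays within one couple of 20/20 at least 99% of the time for the cohort sizes shown.

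**The case against.** The strongest reply is that simple randomisation is an inference. The protocol does not use the term. A list prepared in advance with 20 of each condition would fit both the mechanism and the stated arm sizes, and block details are often kept out of a protocol to protect concealment. A reader might infer that the trial certainly used unrestricted draws; the document does not show that. What stands is narrower: the protocol does describe a method, its plain reading is one draw per couple, and nothing written there restricts it.

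The second reply is that little is lost. This is correct. Splits as uneven as 16/24 still keep 96% efficiency, the protocol presents the study as a pilot not powered for every outcome, and simple randomisation is valid. A reader might infer that chance imbalance distorts every comparison. It does not: it adds no bias, the standard error allows for it, and the models adjust for the baseline value of the outcome. Nor would blocking by cohort switch off the rule in item 13 that adds covariates found to differ between arms, since age, education or income could still differ by chance.

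Third, one might want to stratify also on whether one or both partners have metabolic syndrome. The protocol gives poor support for this. Telephone screening leaves out the biological indicators, some participants may not be in the electronic record system, and how often both partners are affected is something the study sets out to learn. It would also weaken control of the totals: with that second stratum and mixed blocks of 2 and 4 (cohorts of 20 and 25–75% of couples with both partners affected, both assumed), simulation gives exactly 20/20 only about 48% of the time and within one couple about 93%.

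Finally, the class-size range depends on cohort sizes and one class per cohort, neither of which the protocol states. It is an illustration only.

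**Conclusion.** The point holds as a cheap improvement of low severity. If draws are independent at 1:1, the written mechanism misses the planned split in 87.5% of trials (100% − 12.5%), and it protects neither the balance within cohorts nor class size. The statistical cost is about one point of power on average and under four points at 14/26. The practical cost, uneven classes in a feasibility study, is probably the larger one, but its size rests on the assumed cohorts of 20.

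Two stronger conclusions should not be drawn. The protocol does not show that the comparison is invalid or biased. And blocking within cohort does not make 20/20 certain: with varying block sizes it makes a near-equal split very likely.

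**What to change.** Replace the per-couple random digit with a concealed permuted-block list, with the couple as the unit, block sizes varying (for example 2 and 4), stratified by cohort only. Include cohort as a term in the outcome models. Describe 20 couples per arm as the target rather than an assured count. If a list fixed at 20 of each was intended all along, the protocol should say so; that settles the totals but not the balance within cohorts.

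The cost is one generated list and one model term. The downside is that the last assignment in a block can sometimes be guessed by staff who know the earlier ones. Varying the block sizes and keeping them undisclosed limits this. A constant block of 4 would give 20/20 for certain if each cohort were a multiple of 4, but it is easier to predict, and exact equality is not worth that.

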1. To determine the feasibility of Mindfulness Based Stress Reduction (MBSR) for older cohabiting, intimate couples in which one, or both partners, has metabolic syndrome. We will (a) monitor recruitment, (b) adherence, and (c) missing data for the intervention. We will explore how being a couple impacts the MBSR experience, assessing (a) the prevalence of both partners having metabolic syndrome versus one partner, (b) shared decision making about participation and adherence, (c) how MBSR can be tailored to the needs of older couples, and (d) the impact on relationship quality and shared health behaviors.

2. To determine whether MBSR improves self-reported physical health status (SF-36) (Ware Jr & Sherbourne, 1992) for each partner. Hypothesis 1: The intervention group will have a significantly greater score on the SF-12 scale than does the control group.

3. To determine if MBSR reduces perceived stress (Perceived Stress Scale (Roberti, Harrington, & Storch, 2006)) and increases mindfulness (Kentucky Inventory of Mindfulness Skills (Baer, Smith, & Allen, 2004)). Hypothesis 2: Perceived stress will be reduced and mindfulness will increase for the MBSR group compared to the control group.

4. Exploratory aim: To determine if an MBSR intervention is associated with decreases in the composite measure of metabolic syndrome (blood pressure, waist circumference, glucose levels, cholesterol, triglycerides) for each partner. Hypothesis 3: The metabolic syndrome composite score for partners will be smaller at the end of the study in the MBSR group compared to the control group.

2. Background:

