Accounting for simultaneous participation of couple members in MBSR for manual development. Prior to recruitment, the team will meet with [name], the MBSR instructor to adapt the MBSR manual so that it accounts for couples participating in the classes. Although the MBSR curriculum will not be substantially altered from its validated form, [name] will provide suggestions about how each practice and assignment in the program can acknowledge the partner's presence. We will maintain the standard MBSR program so that it can be easily disseminated to the public in later phases of this research. We are not developing a new relationship oriented MBSR. Rather, we will provide instruction about how each assignment should be carried out knowing that the partner is also in the program at the same time. Upon completion of the study, we will obtain interventionist feedback about how couple participation may have altered the MBSR program. [name] will keep notes about the influence of couple dynamics in her classes throughout the study and summarize them in a team meeting with the PI, Co-Is, and Project manager every 4 weeks and at the end of the study.

Measurement Schedule

	# of items	Variable type	Recruit	Baseline assess	8-week assess
Recruitment					
Referral or chart review: Potential participant has 3 of the following? (a) Abdominal obesity: waist circumference >102 cm in men, >88 cm in women; (b) Hypertriglyceridemia: ≥ 150 mg/dL (1.69 mmol/L); (c) Low high-density lipoprotein (HDL) cholesterol: <40 mg/dL (1.04 mmol/L) in men, <50 mg/dL (1.29 mmol/L) in women; (d) High blood pressure (BP): $\geq 130/85$ mm Hg and/or taking BP medication; (e) High fasting glucose: ≥ 110 mg/dL (≥ 6.1 mmol/L).	1	Inclusion criteria	X		
Participant is 60 or over.	1	Inclusion criteria	X		
Participant married or in romantic relationship?	1	Inclusion criteria	X		
Are they living together?	1	Inclusion criteria	X		
Participant's partner interested in being in the study?	1	Inclusion criteria	X		
Both partners age 60 or over?	1	Inclusion criteria	X		
Either partner non-English speaking?	1	Exclusion criteria	X		
Either partner practice mind-body therapies more than once/week (yoga, meditation)?	1	Exclusion criteria	X		
Either partner taking psychiatric medications?	1	Exclusion criteria	X		
Random assignment to intervention or waitlist control group	1	Intervention/control status			

Self-report Measures (Both partners)					
Socio demographics: age, gender, education, income	4	Covariates		X	X

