Physical health symptoms (SF-12)	12	Primary outcome		X	X
Perceived stress scale (Roberti et al., 2006)	10	Primary outcome		X	X
Kentucky Inventory of Mindfulness Skills (Baer et al., 2004)	39	Primary outcome		X	X
Relationship Assessment Scale (Hendrick, 1988)	7	Secondary outcome		X	X
Health behavior questionnaire (sleep, physical activity, eating behavior, medication adherence (Schulz et al., 1997))	22	Secondary outcome		X	X
Couples' decision making in participation and adherence: 1) How was your partner involved in your decision to first participate in the intervention? (Responses: a. encouraged you, b. discouraged you, c. neither) 2) How was your partner involved in your decision to continue with each class? (Responses: a. encouraged you, b. discouraged you, c. neither) 3) Open ended question: Describe how participating with your partner influenced your experience with the intervention.	3	Exploring couple dynamics			X
Biological Measures (Both partners)					
Blood draw: to assess hypertriglyceridemia and low high-density lipoprotein (HDL) cholesterol and high fasting glucose	3	Secondary outcome		X	X
Abdominal obesity- waist circumference per WHO protocol (2011)	1	Secondary outcome		X	X
Blood pressure (automated Carescape cuff)	1	Secondary outcome		X	X
Do both partners, only the husband, or only the wife have metabolic syndrome at baseline?	1	Exploring couple dynamics			
Feasibility Measures (Both partners)					
Percent of couples who screen versus enroll (Project manager keeps a record.)	1	Feasibility outcome	X		
# of MBSR sessions attended (Interventionist takes attendance.)	1	Feasibility outcome			X
Total minutes of home MBSR practice (Participants keep a daily record.)	1	Feasibility outcome			X

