Hypothesis 3: The metabolic syndrome composite score for participants will be smaller at the end of the study in the MBSR group compared to the control group. Given the exploratory nature of this hypothesis and the lack of consensus as to how to code a variable for metabolic syndrome, this Hypothesis 3 will be analyzed in three different ways: 1) with the outcome as a binary indicator variable indicating the occurrence of 3 or more of the 5 syndrome components; 2) with the outcome as a continuous variable obtained from the summation of Z-score transformations of the 5 syndrome components; and 3) as continuous latent factor or principal component construct obtained from a factor analytic measurement model. Performing these three analyses will provide invaluable insights for determining how the metabolic syndrome outcome will be coded in future studies using older samples.

We will explore the dyadic effects of couple members' simultaneous engagement in the MBSR intervention. In addition to the above analyses, we will use SPSS mixed models for analyzing repeated measures in couples. In this analytic approach, reports of health (primary outcome) (Level 1) are nested within time-invariant individual and couple variables (i.e., background variables, intervention condition (primary predictor), and moderators) at Level 2. The program allows for the analysis of intercepts and slopes of the hypothesized associations between Level 1 variables (i.e., within-couple relations between each partner's health) across all assessment points (baseline, 8 weeks, and 3 months), as well as interactions between Level 2 variables and Level 1 intercepts and slopes. In other words, we will assess whether the intervention was successful at the couple level by looking at the overall intervention effect, as well examine, for heterosexual couples, differential effects for husbands and wives by looking at the role (husband or wife) X intervention interaction.

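### Only the MBSR arm takes partner blood pressure readings at every class, so differences in blood pressure and in the metabolic composite estimate MBSR plus weekly partner monitoring, not MBSR alone

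*Protocol*

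**What the plan says.** In the Protocol, Section I, item 3 (Research Plan), the MBSR condition paragraph gives the number of classes: "MBSR is a standardized protocol consisting of 8-weekly 2.5 hour sessions". It then adds a blood pressure task: "Participants will take their partners blood pressure reading with an automated Carescae cuff at each MSBR class".

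The wait-list paragraph that follows describes no classes during the comparison period: "After the MBSR condition groups have completed their sessions, the participants in the Wait List group may choose to participate in the 8-week MBSR class". In the meantime, "participants in the Wait list group will complete the same measures at the same time points" as the MBSR cohorts.

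The Measurement Schedule lists "Blood pressure (automated Carescape cuff") as a secondary outcome for both partners, marked at baseline and at 8 weeks. It has no weekly blood pressure entry. Aim 4 uses a "composite measure of metabolic syndrome (blood pressure, waist circumference, glucose levels, cholesterol, triglycerides"). Item 13 (Statistical Considerations) builds the continuous version of this composite as the "summation of Z-score transformations of the 5 syndrome components", and labels the hypothesis exploratory.

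On the content of the programme, the paragraph on adapting the manual for couples says: "We will maintain the standard MBSR program so that it can be easily disseminated to the public in later phases of this research".

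**The concern.** The arms differ in how often an outcome is measured, and by whom, as well as in whether they receive MBSR. Repeated readings may accustom people to the cuff. Readings taken by a spouse may also draw attention to blood pressure and alter medication-taking or contact with a doctor. Either route could change the 8-week reading without any effect of the mindfulness training.

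Most other components of the programme act on blood pressure only as treatment. This one also repeats the outcome measurement itself, with the same type of device, in one arm only. Adjusting for the baseline value does not remove it, because the extra readings come after baseline. The analyses in item 13 contain no step that separates the two.

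What is at stake is the label on the biomarker results. The Background section (Aim 4) intends them to supply early effect sizes for longer studies of MBSR in older couples. If the readings stay and are not named, a package effect would be carried forward as an effect of MBSR.

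**Working it through.** The protocol states no figure on this point, so there is none to reproduce. The check compares procedures, followed by an illustration of scale.

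**Count of readings per person between baseline and the 8-week visit (inclusive)**

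| | MBSR | Wait list |
|---|---|---|
| Scheduled (Measurement Schedule) | 2 | 2 |
| At classes (MBSR condition) | up to 8 | 0 described |
| Total | up to 10 | 2 |

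The count of 8 is an upper limit. It assumes full attendance, leaves out the retreat, and assumes that all classes precede the visit, although the visit window runs from five to eleven weeks after enrolment. A reading at the 3-month visit, if one is taken, would add one to each arm and leave the difference unchanged.

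**Does the wait-list sentence supply matched readings?** No. It refers to measures and time points, and the schedule contains no weekly reading. The class readings are tied to classes that controls do not attend until the MBSR groups have finished.

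**Does any outcome use the class readings?** The schedule lists none. Blood pressure appears there only as the baseline and 8-week assessment.

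**Weight in the composite.** Blood pressure is 1 of 5 terms in the Z-score sum and 1 of 5 criteria in the binary version (3 or more of 5).

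**Scale, under assumptions that are not in the document.** Suppose the extra readings lower systolic pressure by 2 to 5 mm Hg, with an SD of 15.

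- On systolic pressure: 2/15 = 0.13 SD and 5/15 = 0.33 SD.
- On the sum of five Z-scores, if the components are independent: the SD of the sum is √5 = 2.24. The shift is then 0.13/2.24 = 0.06 SD to 0.33/2.24 = 0.15 SD, and less if the components are positively correlated.
- On the 130 mm Hg cut, with systolic pressure N(135, 15): the share below 130 is Φ(−5/15) = 36.9%. With the mean moved to 133 it is Φ(−3/15) = 42.1%, a rise of 5.1 points before rounding. With the mean moved to 130 it is 50.0%, a rise of 13.1 points.

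The last figures apply only to untreated participants and ignore the diastolic limb. Under the eligibility wording, taking blood pressure medication already meets the criterion, so treated participants cannot change status through lower readings. Nor does crossing 130 by itself change syndrome status, which depends on the other four components as well.

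For comparison, the only detectable difference that the protocol states is for the SF-12: 6.43/10 = 0.64 SD.

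**The case against.** The strongest reply is that couples are randomised, so the arm comparison validly estimates the effect of what is delivered, partner readings included. That stands. A reader might infer that no blood pressure difference could be credited to the programme, or that the comparison is invalid. The text supports neither.

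Second, the control is a wait list, so group contact, instructor time, yoga, the retreat and practice logging are unmatched too. Removing the readings would not isolate mindfulness. This also stands, and it narrows the point to the one component that repeats the outcome measurement.

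Third, the outcomes concerned are secondary or exploratory, and the Background itself doubts that biomarkers will move in so short a time. That limits the weight of the point but does not settle how the effect sizes should be labelled.

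Fourth, the mechanism and its direction are conjecture. The protocol does not say whether class readings are recorded, discussed or acted on. A reader might infer that the readings inflate the MBSR effect. The document does not show this: it gives no size, and an effect in either direction is possible.

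Finally, the manual may be adapted modestly for couples, and a brief partner reading could count as such an adaptation. A contradiction with the promise to keep the standard programme is therefore weak. It remains true that the protocol nowhere names the readings as an added component or states their purpose.

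**Conclusion.** The asymmetry is in the text: up to 8 extra partner-taken readings per person in the MBSR arm and none described in the wait-list arm, on a variable that is a secondary outcome and one-fifth of the composite. It follows that a between-arm difference in blood pressure, and to a smaller degree in the composite, is an effect of MBSR with weekly partner blood pressure monitoring and cannot be attributed to MBSR alone.

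The conclusion rests on two readings: that the misspelled cuff in the class description is the same type as the one in the schedule, and that no unlisted matched readings are planned for controls. It does not rest on the 2 to 5 mm Hg illustration, whose inputs are all assumed. The SF-12 primary comparison is not directly affected, and a reader should not extend the point to it. The change is inexpensive and worth making before biomarker effect sizes are used for planning.

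**What to change.** One of two changes is enough.

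1. Delete the sentence on in-class partner readings. No listed outcome uses them. The cost is the loss of a couple exercise whose purpose the protocol does not state.
2. If the exercise is wanted, state its purpose and describe the intervention throughout as MBSR with weekly partner blood pressure readings. Add to item 13 that the blood pressure and composite results, and any effect sizes taken into later studies, are for this package. The cost is a narrower statement of what the biomarker results show.

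Matched partner readings for wait-list couples would also remove the asymmetry. They would add burden and turn the control into a monitored wait list, so this is a larger change than either of the two above.
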